#### 4.2.12. Visit Windows

Visit windows are defined in Table 2, and are applicable for efficacy (except diary data) and safety.

**Table 2 Evaluation Intervals for Efficacy and Safety Analysis**

Evaluation	Targeted time point	Protocol-Specified Interval	Interval for Analysis
Screening Visit 1	Day -21	Day -21	Day -18 or earlier
Screening Visit 2*	Day -14	Day -16 to Day -12	Day -17 to Day -4
Baseline	Day 1	Day 1	Day -3 to Day 1
Week 2	Day 15	Day 12 to Day 18	Day 2 to Day 22
Week 4	Day 29	Day 26 to Day 32	Day 23 to Day 43
Week 8	Day 57	Day 53 to Day 61	Day 44 to Day 71
Week 12	Day 85	Day 81 to Day 89	Day 72 to Day 99
Week 16 FU	Day 113	Day 108 to Day 118	Day 100 or later

\* At least 6 days after Screening Visit 1 to allow at least 6 days of paper diary data to be completed. Study day is calculated per section 4.2.8.

In case more than one measurement per time period is captured, the closest to the targeted time point will be considered for analysis. If two measurements occur at the same distance from the target day for a particular analysis window then the first measurement will be considered for analysis. Unscheduled visits will be taken into account. In case of withdrawal, all data from the early termination visit will be assigned under its corresponding analysis visit according to its day.

Actual dates and times will be used for pharmacokinetic summaries rather than nominal days and times.

Any visits occurring outside visit windows defined in the protocol should be recorded as a PD and will be reviewed at the BDRM to assess on an individual case by case basis to which visit the data should be allocated.

### 4.3. Interim Analyses

The first IA will be conducted after efficacy data from frequency and severity of HF is collected through Week 4 from 30 patients randomized in equal proportions to the four NT-814 doses and placebo.

Based on DRC review of the IA results, randomization ratios for subsequent enrolled patients may be changed to optimize the allocation of subjects to doses with target levels of weekly average daily HF frequency reduction from baseline of 6 and 8; and HF severity reduction from baseline of 0.66 and 0.88 (Study RELENT-1). Adaptive design algorithm will be based on Bayesian Emax dose-response modelling [1] and / or T-statistic adaptive dose-finding design [2]. The DRC will have dose assignment recommendations by each of those adaptive dose-finding algorithms and assign the randomization ratio that best integrates the objectives of the trial and the adaptive design results. Randomisation ratio recommendations will also take into consideration emerging safety findings as well as the need to allocate sufficient subjects to a dose of interest to enable an adequate assessment of safety to be made.

Subsequent IA's will be conducted similarly, after Week 4 data from each cohort of ~30 additional patients become available.

The DRC will evaluate stopping criteria per the IA algorithms as described in Appendix B of the protocol and decide on stopping assignment of subjects to specific doses or stopping the trial for an efficacy conclusion and dose choice for subsequent study or futility.

The review of efficacy will be based only on the frequency and severity of HF recorded by subjects in the electronic diary (eDiary).

The review of safety will be based on adverse event and early withdrawal information.

For each IA, a cut-off date will be applied such that data will be included until the date the last patient in the analysed cohort completes the Week 4 visit.

#### 4.3.1. Demographic and baseline data

Demographic data and menopause characteristics will be summarised by treatment group for the Safety Analysis Set (see sections 4.5.1 and 4.5.2 for the details).

#### 4.3.2. Efficacy analysis

At each interim review, summaries by dose group will be provided on the FAS for each of the following:

- Mean daily frequency of moderate and severe HF at baseline, mean daily frequency of moderate and severe HF at each study week, including Week 4 and mean change and percent change from baseline in the mean daily frequency of moderate and severe HF at each study week.
- Mean severity of moderate and severe HF at baseline, mean severity of moderate and severe HF at each study week, including Week 4, and mean change from baseline in the severity of moderate and severe HF at each study week.

If available, summaries of the same data at later time-points (Week 8 and Week 12) will also be reviewed.

Mean daily frequency at each study visit will be calculated using the same method as the one described in section 4.2.11 based on the last 7 days with at least one available data in the evening and/or morning before the corresponding visit.

Mean weekly severity at each study visit will be calculated using the following:

$$\frac{[(\text{number of mild hot flushes for 7 days}) \times 1 + (\text{number of moderate hot flushes for 7 days}) \times 2 + (\text{number of severe hot flushes for 7 days}) \times 3]}{\text{total number of mild, moderate and severe hot flushes over 7 days}}$$

If the number of hot flushes is equal to 0, then the mean severity will be set to 0.

These 7 last days with available data should be within the 14 days prior to the CRF study visit, so in the following window: [CRF Visit date – 14; CRF Visit date], with at least one day within

the last 7 days prior to the study visit. In case of withdrawal, the day this ET visit happened will be checked to see in which windows it is and then to assign the corresponding timepoint. If a CRF visit has already been done at that timepoint, then the CRF visit date will be used. If less than 7 days fulfil these rules, only the correct data will be used in the derivation, and formula will be adjusted using the right number of days as denominator. Morning diary data on the day of a Visit will be included in the derivation as the morning diary is actually associated with the previous calendar day (a complete day is an evening then a morning diary).

In addition, emerging data will be evaluated via the two adaptive following algorithms to evaluate the emerging data at Week 4:

- (i) a Bayesian adaptive Emax (S-shaped) dose-response model fit, and
- (ii) a model based on isotonic regression (T-stat)

The models have been developed using the following prior assumptions:

1) On frequency of hot flushes:

- The mean reduction in the mean daily number of moderate and severe HF's in the placebo group is 4 per day
- Two target levels of test treatment: mean reduction from baseline in the mean daily number of moderate and severe HF's of 6 and 8
- Common standard deviation (SD) of 4.4
- Stopping guidelines for Emax if (a) the probability is > 90% that the mean hot flush reduction is at least 8 at that dose, or (b) the probability is <20% that the mean hot flush reduction is at least 5 (i.e., >80% probability that the mean hot flush reduction is <5).

2) On severity of hot flushes:

- The mean reduction in the severity of moderate and severe HF's in the placebo group is 0.44 per day
- Two target levels of test treatment: mean reduction from baseline in the severity of moderate and severe HF's of 0.66 and 0.88
- Common standard deviation (SD) of 0.55
- Stopping guidelines for Emax if (a) the probability is > 90% that the mean severity hot flush reduction is at least 0.88 at that dose, or (b) the probability is <20% that the mean severity hot flush reduction is at least 0.22 (i.e., >80% probability that the mean hot flush reduction is <0.22).

Emerging data (mean change from baseline in the frequency/severity of moderate and severe HF at Week 4) will be entered in COMPASS software using the Execute module. The following steps will be followed:

- Raw data from eDiaries will be provided to the Cytel blinded team by ERT, the CRF data will be provided by the Pharm Olam Data Management team
- Efficacy endpoints to be presented (see above) will be generated by the Cytel blinded team using the derivation described in this SAP
- Statistical descriptive tables for these endpoints will be produced by the Cytel blinded team using a dummy randomisation list

- Programs will be rerun by the Cytel unblinded team using the real randomisation list provided to the Cytel unblinded statistician
- Endpoint data for each patient along with their treatment arm will be entered into COMPASS.

Prior distributions, defined above and used for the simulation, will also be entered in the software. COMPASS has been developed as a software package for design of adaptive early stage trials within Cytel's suite of software programs for design, analysis, and implementation of clinical trials.

Outputs from the software after having the randomisation code applied will be provided to the DRC members. The outputs comprise:

- Summary tables showing: subject allocation, observed and model-estimated mean results, by dose and pooled SD's, posterior probability (for Emax) or conditional power (for T-stat) and summary statistics
- New subject data with a new recommended randomisation ratio, considered the most efficient per the method.

A summary of the results provided by COMPASS included the allocation probability (related to the next randomisation ratio) recommended from the Emax and T-stat analyses, based on the frequency and severity of HF, will be provided by the unblinded statistician to the DRC members in a separate report. The DRC will take into consideration these results in recommending the randomisation ratio for the next cohort of subjects.

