#### 4.2.11. Baseline definition

Baseline is defined as the data most recently collected prior to the first randomised treatment intake date/time. If time of the corresponding data (e.g. Questionnaires) is not collected then, we will assume that the assessment at Visit 3 is performed as planned, i.e. prior to the treatment intake.

The baseline assessment for hot flushes will be calculated using the last 7 days (not necessarily consecutive days) with an available data in the evening and/or the morning of the baseline diary completion period. A diary day is comprised of the evening entry of this day and the morning entry of the following day, in that order.

Mean daily frequency = Sum of number of hot flushes filled in the diary during the last 7 diary days (with at least one available data in the evening and/or morning) divided by 7.

Mean weekly severity = (number of moderate hot flushes for 7 days) x 2 + (number of severe hot flushes for 7 days) x 3] / (total number of moderate to severe hot flushes over 7 days).

Mean daily HF score = Sum of (frequency x severity) filled in the diary during the last 7 days (with at least one available data in the evening and/or morning) divided by 7. Severity is graded by the women from 1 to 3 (1 = mild; 2 = moderate; 3 = severe).

For the primary efficacy endpoint analyses and several of the secondary endpoint analyses, only moderate and severe HF data are included in the calculations. For these analyses the mild data recorded in the diary will be excluded from the baseline values.

A diary day comprises an evening entry and a morning entry, in that order. If a diary has been completed on a particular day but is missing data on HF that day, then it will be assumed that there was no HF on that day. This diary will not be used for the 7 days of baseline data. Only diary with available data will be used in baseline derivation.

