#### 4.6.1. Co-primary analysis

The co-primary endpoints are the change from baseline in the mean daily frequency and mean weekly severity of moderate and severe hot flushes at Weeks 4 and 12.

For each timepoint (Baseline, Week 1, Week 2, Week 4, Week 8, Week 12) summaries will be produced which use data from the 7 days with at least one available eDiary data entry in the evening and/or the morning before the Visit date:

- These 7 days do not need to be consecutive.
- As the data entered in the morning diary is assigned to the previous calendar day (a diary day comprises an evening and a morning entry, in that order) the morning diary with the same calendar date as the Visit day may be included in the calculation.
- For Week 1, the first 7 post-baseline days with at least one available data in the evening and/or the morning will be used.

The methods for calculating the endpoint are the same as described in section 4.2.11.

Absolute and changes from baseline in the mean daily frequencies and mean weekly severity of moderate and severe hot flushes will be summarised by treatment group. Percent changes from baseline in the mean daily frequencies will be also summarised.

The change from baseline will be calculated as follow:

Mean daily frequency (or mean severity) at week 4 (or Week 12) – Mean daily frequency (or mean severity) at baseline.

The percent change from baseline will be calculated as follow:

(Change from baseline / Mean daily frequency at baseline) \* 100.

The mean change from baseline and the corresponding 95% confidence interval (CI) will be displayed graphically by visit on the observed values and by treatment groups.

Bar graphs of the change from baseline at Week 4 and Week 12 will be produced for each treatment group.

The change from baseline endpoint will be analysed using a Mixed-Effect Model Repeated Measures (MMRM) incorporating post-randomization data collected up to treatment discontinuation at weeks 12 (Week 1, 2, 4, 8 and 12 will be included; Week 16 visit data will not be included in the model) and with consideration of the variance-covariance matrix of the repeated measures.

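### Interim severity change subtracts a baseline that leaves out mild flushes from a visit score that counts them, so an unchanged diary can show a reduction

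*SAP*

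**What the plan says.** - **Baseline (SAP 4.2.11).** Severity is (2 × moderate + 3 × severe) divided by the "total number of moderate to severe hot flushes over 7 days". For the primary endpoint analyses and several secondary ones, the section adds: "For these analyses the mild data recorded in the diary will be excluded from the baseline values".
- **Interim visits (SAP 4.3.2).** "Mean weekly severity at each study visit will be calculated using the following": (1 × mild + 2 × moderate + 3 × severe) divided by the "total number of mild, moderate and severe hot flushes over 7 days". It continues: "If the number of hot flushes is equal to 0, then the mean severity will be set to 0".
- **Label and use (SAP 4.3.2).** The summary bullets and the software step both call the result the change in severity of moderate and severe flushes. The Week 4 change is entered in COMPASS with these settings: "Two target levels of test treatment: mean reduction from baseline in the severity of moderate and severe HF's of 0.66 and 0.88", a placebo reduction of 0.44 and an SD of 0.55. The Emax stopping guidelines are a probability above 90% that the reduction is at least 0.88, or below 20% that it is at least 0.22. The resulting allocation recommendations, for frequency and for severity, go to the DRC.
- **Final analysis (SAP 4.6.1).** For the co-primaries: "The methods for calculating the endpoint are the same as described in section 4.2.11".
- **Frequency.** SAP 4.3.2 derives interim frequency by the 4.2.11 method, so only severity has a second formula.
- SAP 5 reports no changes from the protocol analyses and does not mention the difference.

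**The concern.** The two formulas give different scores for the same diary whenever mild flushes are recorded. Subtracting a moderate/severe-only baseline from a visit score that includes mild flushes gives a change that is partly real and partly the woman's mild share. That quantity does not match its label, and it is not what SAP 4.6.1 tests at the end of the study.

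It matters because interim severity is judged against absolute reductions. An offset common to all arms would cancel in a contrast with placebo, but not against 0.22, 0.66 or 0.88. The outputs help the DRC to change randomisation ratios and to stop assignment to a dose, and allocations made on that basis cannot be undone.

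**Working it through.** **The plan's own figures.** The SAP states no sample size or power for severity. Its pairwise figure of 33 per group is for frequency (difference 8 − 4 = 4, SD 4.4, two-sided 0.05). It reproduces, with noncentral-t power of 0.947 at 32 and 0.953 at 33. Nothing below depends on it.

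**Algebra.** Let S0 and S1 be the 4.2.11 scores (moderate and severe only) at baseline and at the visit, and p the share of all visit flushes that are mild. The 4.3.2 visit score is p × 1 + (1 − p) × S1 = S1 − p(S1 − 1). The interim change is therefore

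(S1 − S0) − p(S1 − 1).

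The first bracket is the co-primary change. The second term comes only from counting mild flushes at the visit. For an unchanged diary S1 = S0, and the change is −p(S0 − 1).

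**Example (assumed counts).** 14 mild, 35 moderate and 35 severe flushes a week at both times:
- baseline: (70 + 105)/70 = 2.50
- visit: (14 + 70 + 105)/84 = 2.25
- change: −0.25, where p = 14/84 = 16.7% and 0.167 × 1.5 = 0.25

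With either formula used at both times the change is 0.

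**Mild share at which the artefact alone reaches each figure**, p = threshold/(S0 − 1). The documents give neither p nor S0, so S0 is varied:

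| Assumed S0 | 0.22 (low-response guideline) | 0.44 (assumed placebo response) | 0.66 (lower target) |
|---|---|---|---|
| 2.2 | 18.3% | 36.7% | 55.0% |
| 2.4 | 15.7% | 31.4% | 47.1% |
| 2.5 | 14.7% | 29.3% | 44.0% |
| 2.8 | 12.2% | 24.4% | 36.7% |

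**Effect on the low-response guideline.** I use a flat-prior normal approximation for a single dose with SD 0.55, standing in for the vague-prior Emax fit. The first interim has 30 subjects in five equal arms, so 6 per arm; the simulated total of 150 gives 30 per arm. The guideline is met when the probability of a reduction of at least 0.22 is below 20%.

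| Mean reduction entered | n = 6 | n = 30 |
|---|---|---|
| 0 (no true change, one formula) | 0.164, met | 0.014, met |
| 0.25 (no true change, formulas as printed, example above) | 0.553, not met | 0.617, not met |

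**Scale of the inputs.** While any moderate or severe flush remains, the 4.2.11 score is at least 2, so the largest possible individual fall is S0 − 2. An individual fall of 0.88 then needs S0 of at least 2.88. SAP 4.3 attributes the 0.66 and 0.88 targets to RELENT-1 but does not say how severity was scored there.

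**Visits with no moderate or severe flush.** The 4.2.11 formula is 0/0. The 4.3.2 formula gives 1 if only mild flushes remain, and its zero rule gives 0 if there are none.

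**The case against.** **Other readings of the text.** SAP 4.2.11 says that only moderate and severe data enter the primary calculations, and 4.3.2 repeats that label. One could therefore take the printed formula as a general template whose mild term drops out. But 4.3.2 lists only moderate-and-severe severity measures, so the mild term would have no use there, and it tells the programmers to follow the SAP derivation. Baseline is also a visit. If the 4.3.2 formula covers it, the false reduction goes, but 4.2.11 is contradicted and the measure is still not the co-primary. SAP 3.2 cites 4.3.2 for the diary-day rules. If the formula also carried into the final analysis, the mismatch would move into the co-primary, against 4.6.1. Each reading leaves a conflict. What does stand is that the text cannot show which formula was programmed.

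**Size.** It is assumed throughout. Women who record no mild flushes are unaffected, and nothing in the documents supports any particular mild share. This stands, which is why thresholds are shown rather than an estimate.

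**Consequence.** Frequency is derived consistently, and the DRC also weighs safety and the trial objectives. The severity cut-offs are guidelines. The T-statistic dropping rule in protocol Appendix B is relative to placebo, so an offset equal across arms would cancel there. All of this limits the harm. It does not help with the absolute guidelines and targets, nor if mild shares differ between arms.

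**An inference to avoid.** A reader might argue that the interim score is wrong because it can move opposite to the co-primary. Take 6 moderate and 4 severe at baseline (2.40), then 5 mild, 1 moderate and 2 severe. The interim score falls to 13/8 = 1.625 (−0.78), while the 4.2.11 score rises to 8/3 = 2.67 (+0.27). This woman has no mild flushes at baseline, so counting mild at both times also gives −0.78. The disagreement is a property of a moderate/severe-only endpoint, which rises when moderate flushes become mild. It is not evidence of the baseline/visit mismatch.

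**Conclusion.** The point holds on the text as printed. SAP 4.2.11 and 4.3.2 give incompatible severity formulas for the two ends of one change score, and the result is neither the quantity named nor the 4.6.1 co-primary. An unchanged diary yields a false reduction of p(S0 − 1). For an assumed S0 of 2.2 to 2.8 it reaches 0.22 at mild shares of about 18% to 12%. At S0 = 2.4 it reaches 0.44 at about 31%.

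Three stronger conclusions are not supported:
- **That the final test is biased.** Under 4.6.1 it uses the 4.2.11 method at every time point.
- **That doses were in fact favoured or dropped wrongly.** The documents show neither the interim data nor the program used, and severity is one of two efficacy inputs.
- **That the severity inputs are on the wrong scale, or that 0.88 is unattainable.** The 2.88 bound applies to an individual with a remaining moderate or severe flush. The targets are means, and under 4.3.2 women with no flushes score 0. The scale is unverified, not shown to be wrong.

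**What to change.** 1. In SAP 4.3.2, replace the visit severity formula with the 4.2.11 moderate/severe-only formula, so that baseline, interim and final co-primary share one definition. Counting mild flushes throughout would also be consistent, but carried to the final analysis it would change the protocol's co-primary endpoint.
2. State one rule, applied at interim and final, for a visit with no moderate or severe flushes, covering both the mild-only and the no-flush case.
3. Report the mild-inclusive score only as severity of all hot flushes, with mild counted at baseline too.
4. Confirm that 0.22, 0.44, 0.66, 0.88 and the SD of 0.55 were derived on the moderate/severe-only scale, and correct them if not.
5. If interims have already been run, state which formula was used and rerun the severity outputs on the consistent one. This SAP already reports blinded-review outcomes in the past tense (3.1 and 4.6.2.7), so this may be the step that applies. A rerun cannot undo allocations, but it shows whether the recommendations would have differed.

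The cost is SAP wording, one derivation and, if needed, a rerun of COMPASS for severity. No new trial data are required. If the inputs prove to be on another scale, re-deriving them would need the RELENT-1 severity data, which are not in the documents.

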#### 4.2.7. Missing, Unused, and Spurious Data

In general, there will be no substitutions made to accommodate missing data points. All data recorded on the CRF will be included in data listings that will accompany the clinical study report.

Sensitivity analyses may be performed, and are detailed in the corresponding efficacy endpoint sections.

Clinical laboratory values as “<X” where X is the numerical value of the limit of quantification (LOQ) established by the laboratory will be imputed by LOQ/2 for summaries in the tables.

Clinical laboratory values as “>X” where X is the numerical value of the limit of quantification (LOQ) established by the laboratory will be imputed by LOQ for summaries in the tables.

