- lsmeans_: LSM, SE and 95% CI for each treatment at each visit  
- diffs_: Difference in LSM, 95% CI and p value  
- tests3_: overall p values for the fixed effects.
```

The assumption of normality (to ensure that the parametric models are appropriate) will be explored via the visual checks that are based on a normal probability plot of the residuals against their values expected on the normal distribution. If the data are normally distributed then the residuals will roughly form a straight line on the normal plot. If the plotted data deviates markedly from a straight line then it is likely that the data are not normally distributed. In that case, a non-parametric analysis will be used as a sensitivity analysis to complement the parametric MMRM results. A Wilcoxon rank-sum test will be performed at each timepoint (Week 4 and 12) and for each pairwise treatment comparison.

SAS code:

```
PROC NPARIWAY DATA= dataset WILCOXON;  
CLASS treat;  
VAR chg;  
EXACT Wilcoxon;  
WHERE avisit = "Week 4" and treat in ("Placebo","NT-814 40mg");  
RUN;  
* chg represents the mean change from baseline variable;  
* treat represents the treatment group;  
* avisit represents the analysis visits as defined in section 4.2.12.
```

In addition, as a sensitivity analysis, an analysis of covariance (ANCOVA) including terms for treatment group, along with the following baseline covariates: Baseline frequency or severity, Region (section 4.2.3). This analysis will be performed at each timepoint (Week 4 and Week 12).

SAS code:

```
PROC MIXED DATA=dataset;
CLASS treat region;
MODEL chg = treat base region;
LSMEANS treat / pdiff (ref='Placebo') cl;
ODS OUTPUT lsmeans=lsmeans_ tests3 = tests3_ diffs = diffs_
convergenceStatus=convergenceStatus_;
WHERE avisit = "Week 4";
RUN;
* base represents the baseline value of the endpoint;
* chg represents the change from baseline variable;
* treat represents the treatment group;
* region represents the categorical covariate related to stratification factors.
Further options to control the output may be added. See MMRM notes for ODS
OUTPUT.
```

As an ad-hoc analysis, treatment mean comparisons to placebo may be made via estimated means from a 4-parameter Emax model fit and trend test for increasing response with increasing dose based on isotonic regression modelling at Week 4 and Week 12 using the same methodology as described in section 4.3.2.

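### Severity endpoint: the interim formula counts mild flushes that the baseline excludes, and the final co-primaries have no stated value for a week with no moderate or severe flushes

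*SAP*

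**What the plan says.** Two of the four co-primary endpoints are change in severity of moderate and severe hot flushes, at Weeks 4 and 12. Protocol 11.1.1 requires all four co-primaries to be significant for a firm conclusion of benefit.

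- **Baseline (SAP 4.2.11).** Severity weights moderate flushes 2 and severe flushes 3, and divides by the "total number of moderate to severe hot flushes over 7 days". For the primary endpoints, "only moderate and severe HF data are included in the calculations", and mild entries are left out of the baseline value.
- **Interim visits (SAP 4.3.2).** The endpoint is named as severity of moderate and severe flushes. The formula printed for each study visit nevertheless adds mild flushes with weight 1 and divides by the "total number of mild, moderate and severe hot flushes over 7 days". It is followed by: "If the number of hot flushes is equal to 0, then the mean severity will be set to 0".
- **Final visits (SAP 4.6.1).** "The methods for calculating the endpoint are the same as described in section 4.2.11". Neither 4.6.1 nor 4.2.11 gives a value for a week whose denominator is zero.
- **Missing data (SAP 4.2.7).** "In general, there will be no substitutions made to accommodate missing data points".
- **Other references to 4.3.2.** SAP 3.2 cites it for which diary days count. The optional ad-hoc analysis in 4.6.1 is "based on isotonic regression modelling at Week 4 and Week 12 using the same methodology as described in section 4.3.2".
- **Severity of all flushes (SAP 4.6.2.1).** This secondary endpoint is also sent to 4.2.11, whose severity formula has no mild term.

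**The concern.** There are two separate faults.

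At the interim, the literal derivation subtracts a baseline without mild flushes from a visit value that includes them. Any recorded mild flush then pulls the visit score down and looks like improvement. The result is entered in COMPASS and compared with the severity targets and the Emax stopping guidelines. If the mild terms were meant to drop out, the printed formula is wrong.

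At the final analysis, the co-primary formula is clear but undefined for the subjects who respond best. If a subject has no moderate or severe flushes in the week, 4.2.11 gives 0/0. Read with 4.2.7, she has no severity value at that visit and leaves the estimate because she responded. If the interim rule is borrowed, she scores 0. The borrowed sentence may not cover a week with mild flushes only, because it sits under a formula that counts mild flushes. Two competent programmers could produce different primary results from the same diary data.

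Such weeks are plausible. Protocol Appendix B (Methods) reports mean reductions of up to 9 flushes per day from a baseline of about 10 to 12.

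**Working it through.** The plan states no figure for this point, so the two formulas are evaluated directly.

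**1. Interim change for an unchanged diary.** Illustrative daily counts: 5 moderate and 3 severe at both times, with mild flushes varied. The documents give no mild counts.

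Baseline by 4.2.11: (5×2 + 3×3)/8 = 19/8 = 2.375.

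| Mild per day | Visit value by 4.3.2 | Change |
|---|---|---|
| 0 | 19/8 = 2.375 | 0 |
| 1 | (1 + 19)/9 = 2.222 | −0.153 |
| 2 | (2 + 19)/10 = 2.100 | −0.275 |

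The true change is 0 in every row.

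**2. Weeks on which the rules part.** Take a weekly baseline of 35 moderate and 35 severe, so severity is (70 + 105)/70 = 2.50.

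- Visit with 14 mild flushes only: 4.3.2 gives 14/14 = 1.00, a change of −1.50; 4.2.11 gives 0/0.
- Visit with no flushes: 4.3.2 gives 0, a change of −2.50; 4.2.11 gives 0/0.

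**3. Effect on the final treatment difference.** Let B be baseline severity, d the mean reduction among subjects who still have moderate or severe flushes, and p the share of an arm with none. The mean reduction in an arm is

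- d, if those weeks are missing;
- (1 − p)d + pB = d + p(B − d), if they are set to 0.

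With d alike in both arms, the handling changes the active-minus-placebo difference by (excess p) × (B − d).

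Assume B = 2.3 to 2.5. A score built only from weights 2 and 3 cannot fall below 2, so d lies between 0 and B − 2, and B − d between 2.0 and 2.5.

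| Excess of zero weeks on active | Change in severity difference |
|---|---|
| 0 points | essentially 0 |
| 2 points | 0.04 to 0.05 |
| 5 points | 0.10 to 0.125 |
| 10 points | 0.20 to 0.25 |

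For scale, SAP 4.3.2 assumes: "The mean reduction in the severity of moderate and severe HF's in the placebo group is 0.44 per day". Its targets are reductions of 0.66 and 0.88, so the differences from placebo are 0.66 − 0.44 = 0.22 and 0.88 − 0.44 = 0.44. The two handlings differ by 0.22 when the excess is between 0.22/2.5 = 8.8 and 0.22/2.0 = 11.0 points.

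**4. Spread.** With 10% of an arm at zero, the zeros alone contribute an SD of √(0.1 × 0.9) × (2.0 to 2.5) = 0.60 to 0.75. SAP 4.3.2 assumes 0.55.

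**5. Check against the targets.** Without mild flushes and without zeros, the largest possible mean reduction is baseline minus 2. Targets of 0.66 and 0.88 would need mean baselines of at least 2.66 and 2.88.

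**The case against.** The strongest reply is that the SAP prints general formulas and then restricts them. The frequency formula in 4.2.11 does not exclude mild flushes either, yet nobody would count them. On that reading 4.3.2 is a general 1/2/3 formula, the endpoint name removes the mild terms, and the spurious interim change disappears. This does not hold for severity: 4.2.11 prints its own severity formula with no mild term, so the SAP contains two different severity formulas rather than one that is later restricted.

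On zero weeks, the reply is that baseline cannot be 0/0, because inclusion criterion 8 requires an average of at least 7 moderate or severe flushes per day. The rule is therefore needed only after baseline, and 4.3.2 is where visit values are derived. SAP 3.2 also shows that 4.3.2 reaches beyond the interims, and a completed diary recording no flushes is not a missing data point. The 0.66 and 0.88 targets are out of reach at the assumed baselines unless zeros or mild flushes count. These points make set-to-0 the more likely intention. They do not put it in the final-analysis text: SAP 3.2 borrows only the choice of diary days, and 4.6.1 points to 4.2.11. The argument from the targets also shows how much depends on the convention.

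Three points stand. The interim output only advises the Data Review Committee, and the SAP describes blinded review steps as already done, so the interim part may now be a matter of documentation. The ad-hoc reference to 4.3.2 may mean only the model fitting. The sizes above rest on assumptions.

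**Conclusion.** The concern holds on both parts. As written, the interim severity change compares unlike quantities, and the final severity co-primaries have no stated value for a subject whose moderate and severe flushes have stopped.

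The size cannot be fixed from the documents, which give neither mild counts, nor mean baseline severity, nor the share of zero weeks. For an assumed baseline of 2.3 to 2.5, the choice of handling can move the severity difference by about as much as the lower target difference once the excess of zero weeks on active reaches roughly 9 to 11 points. With no excess it hardly matters. This is arm-mean arithmetic; the MMRM may recover part of the loss from other visits. The planned ANCOVA and Wilcoxon analyses would use the same severity values, so they do not test the point.

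It must be settled before unblinding, because a later choice could be steered by the results.

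**What to change.** 1. Use one formula, moderate and severe only, for baseline and every visit, interim and final.
2. State in 4.2.11 and 4.6.1 that severity is 0 for any week with diary data but no moderate or severe flushes, including weeks with mild flushes only. This extends the SAP's own interim rule.
3. Add a sensitivity analysis with those weeks missing, and report the proportion at zero by arm at Weeks 4 and 12, so that readers can see how much of the severity effect comes from them.
4. Assign the mild-inclusive formula, with a mild-inclusive baseline, to the secondary endpoint on severity of all flushes.
5. Record which formula any completed interim used.

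The cost is SAP wording, one derivation rerun on existing diary data, one sensitivity table and a short note on completed interims. No new trial data are needed.
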